5.2.3 Evaluation during pembrolizumab treatment period

The following assessment will take place within 3 days of each scheduled pembrolizumab treatment between week 7 and 19:

1. Adverse events
2. Vital signs
3. Concomitant medications
4. ECOG performance status
5. Directed physical examination
6. Laboratory tests (FBE, UECr, LFTs). A TSH, T3, T4 is taken every 6 weeks
7. Radiological evaluation (CT Chest/Abdo/Pelvis) at week 19
8. Cystoscopy assessment at week 19
9. Urine cytology at week 19
10. Collection of blood and urine samples for biomarker studies at Week 7

Note that biomarker blood and urine samples are to be taken on Week 7 of therapy with pembrolizumab prior to therapy, please refer to the PCR-MIB Biomarker Laboratory Manual for further blood sampling information.

5.2.4 Evaluation at end of treatment visit (Week 23 or when patient ceases treatment)

The following assessment will take place at the end of treatment visit, when a patient ceases treatment for progression, unacceptable toxicities or any other reason:

1. Adverse events
2. Vital signs
3. Concomitant medications
4. ECOG performance status

5. Directed physical examination
6. Laboratory tests (FBE, UECr, LFTs). A TSH, T3, T4 is taken every 6 weeks
7. Radiological evaluations (CT Chest/Abdo/Pelvis)*
8. Cystoscopy assessments*
9. Urine cytology*
10. Documentation of new anticancer therapies
11. Documentation of disease status
12. Collection of blood and urine samples for biomarker studies

* CT chest/abdomen/pelvis, cystoscopy and urine cytology only need to be performed at End of Treatment visit if these assessments have not been performed at Week 19, for instance if the patients has come of study for toxicity prior to Week 19.

5.2.5 Evaluations at post treatment review visit (Week 31 or 12 weeks post last treatment)

1. Adverse Events
2. Vital signs
3. ECOG performance status
4. Directed physical examination
5. Laboratory tests (FBE, UECr, LFTs). A TSH, T3, T4 is taken every 6 weeks
6. Radiological evaluation
7. Cystoscopy assessment
8. Urine cytology
9. Documentation of new anticancer therapies
10. Documentation of disease status
11. Survival status

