3.2 Secondary Objectives, Hypothesis & Endpoint

Objectives:

- (1) To evaluate the efficacy of the addition of pembrolizumab to concurrent chemoradiation regimen by estimating the complete response rate (see below).
- (2) To characterize:
 - a. overall survival (OS);
 - b. metastatic disease-free survival (MDFS); and
 - c. locoregional progression free survival (LRPFS).

Hypothesis: The addition of pembrolizumab will improve the efficacy of chemoradiation in patients with bladder cancer.

Endpoints:

- (1) Best response, defined as the better of the responses achieved at either the 1st or 2nd cystoscopic examination after completing therapy. (The 1st and 2nd cystoscopic

examinations take place during weeks 19 and 31 respectively of the trial.) See section 7.1.2.6.2 for definitions of the response levels.

(2) Dates of

- i) death,
- ii) detection of metastatic disease,
- iii) detection of locoregional progression,
- iv) any initiation of any new non-protocol anti-cancer therapy

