- g. Patients should have a negative urine or serum pregnancy test within 72 hours prior to receiving the first dose of study medication.
- h. Adverse Events: To be graded according to the NCI Common Terminology Criteria for Adverse Events Version 4.03
- i. Week 7 Pembrolizumab dose will occur in same week as last 2 days of radiotherapy
- j. End of treatment review occur either at Week 23, or 28 days after last treatment for patients who discontinue for either progression before week 19, or other reason i.e. toxicity
- k. CT chest/abdomen/pelvis, cystoscopy and urine cytology only need to be performed at End of Treatment visit if these have not been performed at Week 19, for instance if patients has come of study for toxicity prior to Week 19.
- l. Follow Up visits will be 3 monthly for 12 months after the End of Treatment visit, then 6 monthly for 18 months, then 12 monthly thereafter under study closure, with cystoscopic assessment, urine cytology collection and CT C/A/P within 28 days of each follow up visit. Patients with either local or distant progression do not require vital sign, directed physical examination, urine cytology, or cystoscopy assessment at each visit. Patients with local progression should continue to receive radiological evaluation for assessment of distant metastatic disease. Patients with distant progression should receive radiological evaluation at the discretion of the investigator

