7.1.2.6.2 Cystoscopic Assessment

Assessment of disease with cystoscopy will take place within 42 days of commencement.

The initial re-evaluation will take place 12 weeks (week 19 of trial) after completing chemoradiotherapy (+/- 7 days) (week 19 of the trial). Evaluation will include urine cytology, rigid cystoscopy, tumour site biopsy if indicated and bimanual examination after TUR.

The second check cystoscopy is mandatory at 24 weeks after completing chemoradiotherapy (+/- 7 days) (week 31 of the trial). Evaluation will include urine cytology, rigid cystoscopy, tumour site biopsy if indicated and bimanual examination after TUR.

In follow up, patients will receive cystoscopic assessment every 3 months for 12 months after week 31, then 6 monthly for 18 months, then 12 monthly until 3 years after the last patient is registered.

Any additional cystoscopic assessment (ie 6 weeks post chemoradiotherapy) is at the clinician discretion.

At the cystoscopic assessments for response (weeks 19 and 31), patients will be determined to have either achieved a Complete Response, Partial Response, Stable Disease or Progressive Disease. The determination will be based upon the results of the urologist assessment of the bladder at cystoscopy, histological parameters and result of most recent systemic imaging, as follows.

Patients will be considered as having a **complete response**, or pT0 response, when: i) the bimanual examination under anesthesia is negative, ii) all the biopsies are negative for any tumor at the site(s) of the pretreatment tumor(s), and iii) there is an absence of metastatic disease on the most recently performed systemic imaging.

Patients will be considered to have a **partial response**, when patients have a lower T stage (depth of invasion of tumour) on tumour biopsy than pretreatment tumour T stage and there is an absence of metastatic disease on the most recently performed systemic imaging.

Patients will be considered to have **stable disease** when patients have the same T stage (depth of invasion of tumour) on tumour biopsy compared to pretreatment tumour T stage and there is an absence of metastatic disease on the most recently performed systemic imaging.

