7.1.4 Other Procedures

7.1.4.1 Withdrawal/Discontinuation

When a participant discontinues/withdraws prior to trial completion, all applicable activities scheduled for the end of treatment visit should be performed at the time of discontinuation. Any adverse events which are present at the time of discontinuation/withdrawal should be followed in accordance with the safety requirements outlined in Section 7.2 - Assessing and Recording Adverse Events.

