7.1.6.1 End of Treatment and Post Treatment Review Visits

Visit requirements are outlined in Section 6.0 - Trial Flow Chart for both the

- 1) End of Treatment visit (week 23)
- 2) Post Treatment Review visit (week 31)

The end of treatment visit must be completed within 30 days of ceasing treatment. The post treatment review must be completed 12 weeks post ceasing treatment.

Specific procedure-related details are provided for this period in Section 6.

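### The protocol gives two conflicting clocks for the response cystoscopies of patients who stop treatment before week 19, and does not say which examinations count towards complete response.

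*Combined protocol and SAP*

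**What the plan says.** **Endpoint sections.** Section 3.2 defines the first secondary endpoint as "Best response, defined as the better of the responses achieved at either the 1st or 2nd cystoscopic examination after completing therapy", and its next sentence places those examinations in weeks 19 and 31. Section 5.3.1.4.4 gives the same two weeks. Section 7.1.2.6.2 puts the first re-evaluation 12 weeks after completing chemoradiotherapy, within 7 days either side, and continues: "The second check cystoscopy is mandatory at 24 weeks after completing chemoradiotherapy (+/- 7 days) (week 31 of the trial"). None of these makes an exception for early stoppers.

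**Visit sections.** Early stoppers are put on a different clock.

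- Section 5.2.4 is headed "Evaluation at end of treatment visit (Week 23 or when patient ceases treatment"). Flow chart footnote j says "End of treatment review occur either at Week 23, or 28 days after last treatment for patients who discontinue". Section 7.1.6.1 allows up to 30 days, and section 7.1.4.1 says "all applicable activities scheduled for the end of treatment visit should be performed at the time of discontinuation".
- On content, footnote k says "cystoscopy and urine cytology only need to be performed at End of Treatment visit if these have not been performed at Week 19"; CT is under the same condition. Its example is a patient who came off for toxicity before then. The note to section 5.2.4 agrees.
- The post-treatment review also includes cystoscopy. Section 5.2.5 is headed "Evaluations at post treatment review visit (Week 31 or 12 weeks post last treatment"), and section 7.1.6.1 is firmer: "The post treatment review must be completed 12 weeks post ceasing treatment".

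**Counting rule.** Sections 4.2.4.1 and 8.1 define CR as pT0 at the 1st or 2nd cystoscopic examination, without a week in the definition. Section 2.0 refers to the first two assessments after chemoradiotherapy, at 19 and 31 weeks.

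**The concern.** A site with a patient who stops early can follow either set of rules and comply with the protocol. Under the visit rules, a cystoscopy done well before week 19 is, by order, the first examination after therapy, and the review cystoscopy is the second. A later examination close to week 31 would then be the third and would not count. Under the endpoint sections, the same patient is assessed in weeks 19 and 31.

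The situation is foreseeable. Section 5.3.2.2 lets cisplatin and radiation continue despite pembrolizumab-related events, and Table 6 requires permanent discontinuation of pembrolizumab for several of them. The time at which CR is judged would then depend on whether and when a patient had toxicity, and the 30 outcomes would not share a common clock. CR is a secondary endpoint, but section 8.2 gives it a formal decision threshold in a sample where a few patients can change the decision.

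**Working it through.** **1. The plan's own figure.** Section 8.2 sets the threshold at 18 CRs of 30 and states a 10% chance of judging the regimen worthy at a true rate of 0.5 and 84% at 0.7. With X ~ Binomial(30, p):

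- P(X ≥ 19) = 10.0% at p = 0.5 and 84.1% at p = 0.7, which matches.
- P(X ≥ 18) = 18.1% and 91.6%, which does not.

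The stated figures therefore correspond to more than 18 CRs, and 19 or more is used below.

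**2. Timing under the visit rules.** Radiotherapy ends in week 7 (footnote i). Pembrolizumab is given in weeks 1, 4, 7, 10, 13, 16 and 19 (section 5.3.3). For last treatment week L, the end-of-treatment visit is at L + 4 (footnote j) and the review at L + 12 (section 7.1.6.1). Subtracting 7 gives weeks after chemoradiotherapy.

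| Last treatment (week) | End-of-treatment visit: week (weeks after chemoradiotherapy) | Review: week (weeks after chemoradiotherapy) |
|---|---|---|
| 7 | 11 (4) | 19 (12) |
| 10 | 14 (7) | 22 (15) |
| 13 | 17 (10) | 25 (18) |
| 16 | 20 (13) | 28 (21) |
| 19 (as planned) | 23 (16) | 31 (24) |

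With a last treatment in week 16, a week-19 cystoscopy can still precede the end-of-treatment visit, and in that case footnote k requires no cystoscopy at that visit. With a last treatment in week 19, the response cystoscopies are those of weeks 19 and 31, as intended. If the end-of-treatment visit is held at cessation (sections 5.2.4 and 7.1.4.1), its cystoscopy is earlier than shown. Both examinations fall before week 19 only when all treatment stops before week 7; a last treatment in week 4, for example, gives weeks 8 and 16.

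**3. What is lost.** A patient who completes chemoradiotherapy still has a counted examination at 12 weeks or later. The second look moves from 24 weeks to 12, 15, 18 or 21. For a last treatment in week 7, the first 3-monthly follow-up (section 5.2.6) falls near week 19 + 13 = 32. That is close to the intended 24-week look but is third in order.

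**4. Illustration of size.** The documents give neither the number of early stoppers nor the effect of timing on scored CR, so both are assumed. Let m patients stop early and be scored CR with probability q, and let the other 30 − m have CR probability 0.70. The table gives P(A + B ≥ 19) with A ~ Binomial(30 − m, 0.70) and B ~ Binomial(m, q).

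| q | m = 0 | m = 3 | m = 6 | m = 9 |
|---|---|---|---|---|
| 0.63 (10% of their CRs missed: 0.70 × 0.90) | 84% | 82% | 80% | 77% |
| 0.60 | 84% | 81% | 78% | 74% |
| 0.50 (29% missed: 1 − 0.50/0.70) | 84% | 78% | 70% | 61% |

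The q = 0.50 row is severe: it needs 29% of these patients' responses to be missed at both counted examinations. All rows assume that the change in timing can only lose responses.

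**The case against.** The strongest reply is that weeks 19 and 31 are already fixed. Section 3.2 states them directly after the definition of best response. Section 7.1.2.6.2 assigns response at those weeks, calls the second examination mandatory and treats other cystoscopies as additional. On that reading the end-of-treatment cystoscopy of an early stopper is a clinical examination outside the endpoint. This is a fair reading, and it is why the point is a contradiction rather than a settled rule of early assessment. It does not remove the problem: section 7.1.6.1 is also mandatory in tone, footnote k was written for patients stopping before week 19, and sections 4.2.4.1 and 8.1 count by order.

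A reader might infer more than the documents support:

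- **That early stoppers in general are examined at weeks 11 and 19.** This holds only for a last treatment in week 7.
- **That CR is judged too early in these patients.** CR is the better of two examinations, and in the week-7 case the second is still at 12 weeks, the protocol's own first response time. The slow-responder remark in section 4.1.2 contrasts evaluation after about 40Gy with evaluation 4 to 6 weeks after definitive chemoradiotherapy, which it treats as the late one. It does not argue for 24 weeks over 12.
- **That the CR count is biased downwards.** An early look can miss a slow responder, but a CR seen early counts even if tumour has returned by week 19. Patients who stop for progression are unlikely to be CRs on either schedule.

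**Conclusion.** The contradiction is real and should be resolved before CR is scored. If sites follow the visit rules, patients who stop before week 19 mainly lose the 24-week look, and the time of assessment depends on toxicity. The week numbers rest on the 28-day and 12-week intervals and on chemoradiotherapy ending in week 7 as scheduled.

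The effect on the CR decision is not established in direction or size. The fall from 84% to between 82% and 61% is an illustration over assumed inputs (3 to 9 early stoppers, scored CR 0.50 to 0.63), not an estimate. If all patients are assessed on the 12- and 24-week windows, the stated 10% and 84% stand, read as 19 or more of 30. The primary toxicity endpoint is not affected by this point.

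**What to change.** 1. Reconcile sections 5.2.4, 5.2.5, 7.1.4.1, 7.1.6.1 and footnotes j and k with sections 3.2, 5.3.1.4.4 and 7.1.2.6.2. Keep the safety visits tied to last treatment. State that response cystoscopy, CT and cytology follow the existing 12- and 24-week windows after chemoradiotherapy in every patient still in follow-up, whenever pembrolizumab stopped. Say which date anchors the windows when chemoradiotherapy is not completed.
2. In sections 3.2, 4.2.4.1 and 8.1, define best response by those two windows rather than by order of examination.
3. State how a missing or out-of-window examination, or earlier progression or new anti-cancer therapy, is scored: for example as not CR, with a sensitivity analysis counting all examinations. Without this, defining CR by window would leave some outcomes undefined.
4. State that earlier clinically indicated cystoscopy remains allowed. Whether the end-of-treatment cystoscopy is kept for early stoppers is a clinical decision for the sponsor; the text need only say whether it counts for the endpoint.

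The change is mostly wording in the protocol and its statistical section. The practical cost is that a few early stoppers attend response visits separate from their safety visits, with an additional examination if the end-of-treatment cystoscopy is also kept.

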5.2.6 Evaluations during follow-up

After the end of treatment study visit, patients enter into follow up for OS, LRPFS and DMFS. Follow up for these survival endpoints will be 3 monthly for 12 months after the post treatment review visit, then 6 monthly for 18 months, then 12 monthly until 3 years after the registration of the last patient or study closure. The following assessments will take place at each visit:

1. Vital Signs
2. Directed physical exam
3. Urine cytology
4. Post-study anticancer therapy status
5. Disease Status
6. Survival status

7. Radiological evaluation (CT Chest/Abdo/Pelvis)
8. Cystoscopy assessment

Patients with either local or distant progression do not require vital sign, directed physical examination, urine cytology, or cystoscopy assessment at each visit.

Patients with local progression should continue to receive radiological evaluation for assessment of distant metastatic disease. Patients with distant progression should receive radiological evaluation at the discretion of the investigator.

5.3 Chemoradiotherapy Trial Treatments

The treatment to be used in this trial is outlined below:

Table 3: Trial Treatment

Treatment	Dose	Dose Frequency	Route of Administration	Regimen/Treatment Period
Cisplatin	35mg/m ² (30mg/ m ² if CrCl 40-50)	Weekly, synchronous during radiotherapy	IV infusion	Weekly during radiotherapy for total 6 doses
Radiotherapy	64Gy in 32 fractions	5 daily fractions per week over 6.4 weeks.	3D- Conformal External Beam Radiotherapy	64Gy
Pembrolizumab	200 mg IV	Q3W	IV infusion	Day 1 of each 3 week cycle, until week 12 cystoscopy, for total 7 doses

5.3.1 Trial Treatment Information

5.3.1.1 Cisplatin

5.3.1.2 Description of Cisplatin

Cisplatin is an antineoplastic compound which is a planar inorganic metal salt supplied as a lyophilised powder. It functions as an alkylating agent by producing interstrand and intrastrand crosslinks which modifies DNA structure and prevents DNA synthesis. It also inhibits RNA and protein synthesis.

5.3.1.3 Supply of Cisplatin

Sandoz, Hospira and Pfizer all produce cisplatin. Investigators can nominate to use any brand of Cisplatin that is readily available at their sites. Cisplatin will be provided to study participants according to usual hospital practice, and in Australia will be funded through the Pharmaceutical Benefits Scheme (PBS). Medication labels will be provided by the participating institution's

Pharmacy Department and will comply with requirements of the Australian Therapeutic Goods Administration. Cisplatin will be dispensed as per standard pharmacy practice.

5.3.1.3.1 Administration of cisplatin

Cisplatin chemotherapy will commence on the same day as radiation therapy. After 1000ml sodium chloride 0.9% is administered as prehydration (10mmol MgSO₄ is allowed to be added as per institutional preference), cisplatin 35mg/m² in 1000mL sodium chloride 0.9% will be administered over 60 minutes. Cisplatin is commercially available. Conceivably the co-administration of dexamethasone with the chemotherapy may reduce lymphocyte counts and efficacy of pembrolizumab. Therefore, the dose of dexamethasone administered with chemotherapy will be 4mg IV rather than 8mg unless \geq G2 nausea/vomiting develops. The 5HT3 antagonist palonosetron 0.25mg IV (or equivalent 5HT3 antagonist) will be given prior to cisplatin. Other antiemetic use such as aprepitant and/or olanzapine is permissible. Dexamethasone 4 mg IV premedication given prior to cisplatin is permitted and allowed to continue at dose \leq 4mg orally daily for 2 days after administration. Increase in dexamethasone dose is permitted in discussion with the principal investigator. Urine output measurement is not necessary before cisplatin administration as high urine flow does not appear to be protective.

Cisplatin will be administered weekly during radiotherapy at 7 day intervals

The chemotherapy is to be given preferably at the beginning of each week of treatment and as far as possible on the same day of the week (or within no more than 72 hours) on each occasion throughout the course of treatment.

No more than 6 doses of cisplatin will be administered.

Patients' renal function and myeloid function will be assessed within 72 hours prior to administration of each dose of cisplatin.

The patient should be assessed by the doctor prior to proceeding with each dose of chemotherapy.

Dose modification is described in 5.3.2.1.

5.3.1.4 Pembrolizumab

5.3.1.4.1 Description of pembrolizumab

Pembrolizumab is a novel antibody to PD1, administered intravenously.

5.3.1.4.2 Supply of pembrolizumab

Pembrolizumab will be supplied in the form of 100mg vials. Details of supply, handling and drug accountability are included in the Pharmacy Manual.

5.3.1.4.3 Administration of pembrolizumab

Pembrolizumab 200mg IV, q3 weekly will be given on the same day as the cisplatin, commencing on day 1 (or within no more than 72hrs) of radiotherapy, and given every 3 weeks (weeks 1, 4, 7, 10, 13, 16 and 19).

Pembrolizumab 200 mg will be administered as a 30 minute IV infusion. Sites should make every effort to target infusion duration to be as close to 30 minutes as possible. However, given the variability of infusion pumps from site to site, a window of -5 minutes and +10 minutes is permitted (i.e., infusion duration is 30 minutes: -5 min/+10 min).

Pembrolizumab will continue after chemoradiotherapy has been completed (weeks 7, 10, 13, 16 and 19) for a total of 7 doses for the whole study, culminating with the 7th dose at week 19 of the study (12 weeks post completion of chemoradiotherapy). Pembrolizumab will continue for up to 7 doses total so long as there is

- no evidence of distant metastatic spread before this time
- no intervening administration of new anti-cancer therapy
- no evidence of locoregional progression
- no radiotherapy administered aside from that dictated in the protocol
- no pembrolizumab related AE severe toxicities as detailed in Table 6, Section 5.3.2.2 that require pembrolizumab to be withheld or discontinued.

5.3.1.4.4 Pembrolizumab Adjuvant Treatment

After chemoradiotherapy, patients will receive pembrolizumab in weeks 7, 10, 13, 16 and 19 (radiation will be scheduled for 2 days in week 7, but cisplatin will not be administered).

Pembrolizumab 200mg IV treatment may be administered up to 3 days before or after scheduled the day of each cycle due to administrative reasons but should occur on the same day. Treatment will finish at week 19.

In the event of a treatment delay due to an adverse event outlined in Table 6, patients may resume pembrolizumab within 3 weeks of the due dose. Subsequent dosing of pembrolizumab will continue until week 19, but not beyond this regardless of the total number of doses that the patient has received.

Cystoscopic assessment of tumour response will take place in week 19 and week 31, and is described in Section 7.1.2.6.

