AEs	Grade 3	Withhold or discontinue based on the type of event. Events that require discontinuation include and not limited to: Gullain-Barre Syndrome, encephalitis		confirm etiology and/or exclude other causes		
	Grade 4 or recurrent Grade 3	Permanently discontinue				
1. Withhold or permanently discontinue pembrolizumab is at the discretion of the investigator or treating physician.						
NOTE: For participants with Grade 3 or 4 immune-related endocrinopathy where withhold of pembrolizumab is required, pembrolizumab may be resumed when AE resolves to \leq Grade 2 and is controlled with hormonal replacement therapy or achieved metabolic control (in case of T1DM).						

Dosing of cisplatin and radiation can proceed despite the development of pembrolizumab related adverse events with the exception of the dose modifications described specifically in the sections related to cisplatin and radiation.

Dosing interruptions are permitted in the case of medical / surgical events or logistical reasons not related to study therapy (e.g., elective surgery, unrelated medical events, patient vacation, and/or holidays). Participants should be placed back on study therapy within 3 weeks of the scheduled interruption, unless otherwise discussed with the Coordinating Principal Investigator. The reason for interruption should be documented in the patient's study record.

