5.3.3 Timing of Dose Administration

Pembrolizumab should be administered on Day 1 of commencement of chemoradiotherapy after all procedures/assessments have been completed as detailed on the Trial Flow Chart (Section 6.0).

Pembrolizumab 200mg IV will be given in weeks 1, 4, 7, 10, 13, 16 and 19. Treatment may be administered up to 3 days before or after the scheduled day of each cycle due to administrative reasons.

In the event of a treatment delay due to an adverse event outlined in Table 6, patients may resume pembrolizumab within 12 weeks of the due dose so long as the toxicity has resolved to Grade 1 or less and the patient is on a dose of 10mg or less of prednisolone or equivalent. Subsequent dosing of pembrolizumab will continue until week 19, but not beyond this regardless of the total number of doses that the patient has received.

All trial treatments should be administered on an outpatient basis unless discussed with the Principal Investigator/Sponsor.

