5.5 Rescue Medications & Supportive Care for Pembrolizumab

5.5.1 Supportive Care Guidelines

Participants should receive appropriate supportive care measures as deemed necessary by the treating investigator. Suggested supportive care measures for the management of adverse events with potential immunologic etiology are outlined below. The use of oral or intravenous treatment with corticosteroids as well as additional anti-inflammatory agents if symptoms do not improve with administration of corticosteroids is permitted if necessary. Note that several courses of steroid tapering may be necessary as symptoms may worsen when the steroid dose is decreased. For each disorder, attempts should be made to rule out other causes such as metastatic disease or bacterial or viral infection, which might require additional supportive care. The treatment guidelines below are intended to be applied when the investigator determines the events to be related to pembrolizumab.

Refer to Section 5.3.2.2 for timing for restarting treatment and discontinuation criteria.

It may be necessary to perform conditional procedures such as bronchoscopy, endoscopy, or skin photography as part of evaluation of the event.

- **Pneumonitis:**
 - For **Grade 2 events**, treat with systemic corticosteroids 1-2mg/kg prednisone or equivalent. When symptoms improve to Grade 1 or less, steroid taper should be started and continued over no less than 4 -6 weeks.

- For **Grade 3-4 events, or recurrent Grade 2**, immediately treat with systemic intravenous corticosteroids 1-2mg/kg prednisone or equivalent. When symptoms improve to Grade 1 or less, steroid taper should be started and continued over no less than 4 -6 weeks. Administer additional anti-inflammatory measures, as needed.
- Add prophylactic antibiotics for opportunistic infections in the case of prolonged steroid administration.
- Cisplatin and radiation can continue despite pneumonitis if judged safe by investigators
- **Diarrhea/Colitis:**
 Participants should be carefully monitored for signs and symptoms of enterocolitis (such as diarrhea, abdominal pain, blood or mucus in stool, with or without fever) and of bowel perforation (such as peritoneal signs and ileus).

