 - All participants who experience diarrhea/colitis should be advised to drink liberal quantities of clear fluids. If sufficient oral fluid intake is not feasible, fluid and electrolytes should be substituted via IV infusion. For Grade 2 or higher diarrhea, consider GI consultation and endoscopy to confirm or rule out colitis.
 - For **Grade 2 diarrhea/colitis** that persists greater than 3 days, treat with systemic corticosteroids 1-2mg/kg prednisone or equivalent., then tapering over 4-6 weeks. If Grade 2 diarrhea persists despite steroids for more than 3 days, management should be escalated to treat patient with IV steroids, and pembrolizumab withheld until colitis resolves to Grade 0-1
 - For **Grade 3 or 4 diarrhea/colitis**, treat with systemic intravenous corticosteroids 1-2mg/kg prednisone or equivalent.
 - When symptoms improve to Grade 1 or less, steroid taper should be started and continued over no less than 4 weeks.
- **Type 1 diabetes mellitus (if new onset, including diabetic ketoacidosis [DKA]) or ≥ Grade 3 Hyperglycemia, if associated with ketosis (ketonuria) or metabolic acidosis (DKA)**
 - For **T1DM or Grade 3-4 Hyperglycemia**
 - Insulin replacement therapy is recommended for Type I diabetes mellitus and for Grade 3-4 hyperglycemia associated with metabolic acidosis or ketonuria.
 - Evaluate patients with serum glucose and a metabolic panel, urine ketones, glycosylated hemoglobin, and C-peptide.
- **Hypophysitis:**
 - For **Grade 2** events, treat with corticosteroids. When symptoms improve to Grade 1 or less, steroid taper should be started and continued over no less than 4 weeks. Replacement of appropriate hormones may be required.

- For **Grade 3-4** events, treat with an initial dose of IV corticosteroids followed by oral corticosteroids. When symptoms improve to Grade 1 or less, steroid taper should be started and continued over no less than 4 weeks. Replacement of appropriate hormones may be required as the steroid dose is tapered.
- **Hyperthyroidism or Hypothyroidism:**
Thyroid disorders can occur at any time during treatment. Monitor patients for changes in thyroid function (at the start of treatment, periodically during treatment, and as indicated based on clinical evaluation) and for clinical signs and symptoms of thyroid disorders.
 - **Grade 2** hyperthyroidism events (and **Grade 2-4** hypothyroidism):
 - In hyperthyroidism, non-selective beta-blockers (e.g. propranolol) are suggested as initial therapy.

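### After the same Table 6 adverse-event delay, 5.3.1.4.4 lets pembrolizumab restart within 3 weeks, and 5.3.3 within 12 weeks on two conditions

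*Combined protocol and SAP*

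**What the plan says.** Section 5.3.1.4.4 governs the doses in weeks 7, 10, 13, 16 and 19. For a delay caused by a Table 6 event it states that "patients may resume pembrolizumab within 3 weeks of the due dose". Dosing then runs to week 19, "but not beyond this regardless of the total number of doses that the patient has received".

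Section 5.3.3 lists all seven dosing weeks (1, 4, 7, 10, 13, 16, 19), opens its rule with the same trigger and ends with the same week-19 stop. In between it states that "patients may resume pembrolizumab within 12 weeks of the due dose so long as the toxicity has resolved to Grade 1 or less" and, as a second condition, that "the patient is on a dose of 10mg or less of prednisolone or equivalent".

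Three other places bear on restarting:

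- Section 5.5.1 sends sites elsewhere for timing: "Refer to Section 5.3.2.2 for timing for restarting treatment and discontinuation criteria". The readable part of 5.3.2.2 gives no time limit for Table 6 events. Its note to the table sets a different recovery level for one subset: for "Grade 3 or 4 immune-related endocrinopathy where withhold of pembrolizumab is required, pembrolizumab may be resumed when AE resolves to" Grade 2 or less, with hormonal or metabolic control.
- Section 5.3.1.4.3 continues dosing only while no Table 6 toxicity requires it to be withheld or stopped.
- Section 5.5.1 keeps pembrolizumab on hold in steroid-refractory Grade 2 diarrhea until the colitis is Grade 0 or 1.

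The primary endpoint, unacceptable toxicity (UT), includes a pembrolizumab delay of more than 6 weeks. Items 3.1(e) and 8.1(d) speak only of delay and say that separate delays are not added together. Item 4.2.4.1(b) instead treats it as failure to administer full-dose pembrolizumab without such a delay.

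**The concern.** Both rules apply to doses 3 to 7 under the same trigger, but they differ in the window and in the stated conditions. A site following one section may restart a patient whom a site following the other would not. One window is shorter than the 6-week line in the primary endpoint and the other is longer, so the choice of section can decide whether a dose is given late or not given at all. The endpoint wording does not settle how a dose that is withheld and never given is scored.

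This matters mainly for Grade 2 holds. Table 6 withholds at Grade 2 for pneumonitis, colitis, hepatic events, nephritis and hypophysitis, and such an event is not a UT through its grade. A non-urinary Grade 3 or 4 event within the assessment period already counts.

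**Working it through.** The plan gives no figure of its own for the longest permitted delay, so there is none to reproduce. The check is calendar arithmetic.

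**Inputs.** Dosing weeks 1, 4, 7, 10, 13, 16, 19 (5.3.3). Windows of 3 weeks = 21 days (5.3.1.4.4) and 12 weeks = 84 days (5.3.3). No dosing beyond week 19 (both sections). Endpoint line: more than 6 weeks = more than 42 days (3.1, 4.2.4.1, 8.1).

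**Formula.** For a dose due on day 1 of week *w*, counting from the first missed dose:

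longest delay ending in a restart = min(window, 7 × (19 − *w*) + *e*)

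Here *e* = 0 if dosing must end on day 1 of week 19, and *e* = 6 if it may run to the last day of that week. The documents do not say which.

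| Dose | Week due | 5.3.1.4.4 (days) | 5.3.3, *e* = 0 | 5.3.3, *e* = 6 |
|---|---|---|---|---|
| 3 | 7 | 21 | min(84, 84) = 84 | min(84, 90) = 84 |
| 4 | 10 | 21 | min(84, 63) = 63 | min(84, 69) = 69 |
| 5 | 13 | 21 | min(84, 42) = 42 | min(84, 48) = 48 |
| 6 | 16 | 21 | min(84, 21) = 21 | min(84, 27) = 27 |
| 7 | 19 | 0 (6 if *e* = 6) | 0 | 6 |

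**Reading the table.**

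- Doses 3 and 4: the limits lie on opposite sides of 42 days whichever *e* is used.
- Dose 5: 5.3.3 reaches exactly 42 days with *e* = 0, which is not more than 6 weeks, and passes the line with *e* = 6. It would also pass it, at 42 + 3 = 45 days, if the 3-day administrative allowance applied at week 19.
- Dose 6: the time limits agree with *e* = 0 and differ (21 against 27) with *e* = 6. Neither reaches 42.
- Dose 7: the time limits do not differ.
- Doses 1 and 2 lie outside the weeks listed in 5.3.1.4.4, so only 5.3.3 speaks to them.

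**One patient, two sites.** A Grade 2 event holds the week-7 dose, and both conditions of 5.3.3 are first met at week 15. The delay is 7 × (15 − 7) = 56 days.

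- Under 5.3.3, 56 ≤ 84, so restart is allowed. As 56 > 42, the patient has a UT.
- Under 5.3.1.4.4, the window closed at week 7 + 3 = 10, and the site has no permission from that section. If the withheld dose counts as delayed more than 6 weeks, the score is the same and only treatment differs. If it does not count, the primary endpoint differs too.

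**The case against.** The best case on the other side is that both sentences are permissive. Section 5.3.1.4.4 does not order a stop after 3 weeks, and the mandatory discontinuation list in 5.7 has no delay limit. One could nest the rules: restart freely up to 3 weeks, then up to 12 weeks on conditions. That reading is possible, but no text states it. Section 5.3.3 puts its conditions on the whole 12 weeks, so nesting would still leave the first 3 weeks conditional in one section and not in the other.

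The general-instructions row at the head of Table 6 has no content in the text available here and may hold a governing rule. That is a gap in the copy, not a fault in the plan, and the row should be checked first. Whatever it says, the two sentences would still disagree. The 3-week limit at the end of 5.3.2.2 does not help, because it concerns interruptions unrelated to study therapy.

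Some tempting stronger readings are not supported:

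- *That 5.3.1.4.4 permits restart with no safeguard.* The withholding condition in 5.3.1.4.3 and the colitis condition in 5.5.1 also apply. Only that sentence is unconditional.
- *That a 3-week window is unworkable because* "steroid taper should be started and continued over no less than 4 weeks". The taper runs from improvement and the window from the due dose, and 5.3.3 requires a low steroid dose, not a finished taper.
- *That the delay might be counted from the latest scheduled slot.* With slots 21 days apart, neither window nor the 6-week criterion could then bind, so the plan's own limits would have no effect.
- *That the operating characteristics in 8.2 are wrong.* The documents give no rate for such delays, so no change in the error rates can be shown.

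**Conclusion.** The point stands as an internal inconsistency: the window and the stated conditions differ for the same event and the same doses, and the text is wrong as written. The difference in time limits is 84 − 21 = 63 days for dose 3 and at least 63 − 21 = 42 days for dose 4. It is 21 to 27 days for dose 5 and 0 to 6 days for dose 6, depending on how week 19 is read.

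These figures assume that delay is counted from the first missed dose and that the week-19 stop is absolute. The effect on treatment follows directly from the two texts. A reader might infer that the primary endpoint is necessarily scored inconsistently. That holds only if a dose never given is not counted as delayed; 3.1(e) and 8.1(d) leave this open, and 4.2.4.1(b) can be read as counting it. Few patients are likely to be affected, because most severe events already count as UT by grade, but the documents give no number.

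**What to change.** Check the head row of Table 6 first. The sponsor must then reconcile 5.3.1.4.4 and 5.3.3 on both the window and the conditions, and make the result consistent with 5.3.1.4.3, the note to Table 6 in 5.3.2.2 and the colitis text in 5.5.1. No view is taken here on which window or condition is right. The reconciled text should also say from which date a delay is counted and whether week 19 means its first or its last day.

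In the same amendment, give 3.1(e), 4.2.4.1(b) and 8.1(d) one wording that says whether a dose withheld and never given counts as delayed more than 6 weeks.

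The cost is amendment wording, with no new visits or data. If the aligned wording widens the UT definition, the thresholds in 8.2 (more than 5 of 10, more than 11 of 30) should be rechecked against the 30% and 50% rates.
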